5.2 Exclusion Criteria

- Known HIV, Hepatitis C, or Hepatitis B positivity (subjects with hepatitis B surface antigen [SAg] or core antibody positivity, who are receiving and responding to antiviral therapy directed at hepatitis B or are negative for HBV DNA, are allowed)
- Candidate for potentially curative antibiotic therapy for gastric MALT. (Gastric MALT lymphoma patients with stage I/II H. pylori positive lymphoma must fail therapy with H.-pylori directed therapy before being considered for this study.)
- ECOG performance status 3 or higher.
- Known active CNS involvement.
- Pregnant or lactating females
- Inadequate cardiac function, as measured by left ventricular ejection fraction (LVEF) that is less than or equal to 40%, or the presence of New York Heart Association (NYHA) classification of greater than stage II congestive heart failure.
- Significant neuropathy (Grades 3–4, or Grade 2 with pain) within 14 days prior to screening
- Uncontrolled inter-current illness including, but not limited to, unstable angina, recent myocardial infarction within 6 months of screening and uncontrolled cardiac arrhythmias, psychiatric illness, or psychosocial difficulty that would limit compliance with study requirements.
- Non-hematologic malignancy within the past 3 years with the exception of a) adequately treated basal cell carcinoma, squamous cell skin cancer, or thyroid cancer; b) carcinoma in situ of the cervix or breast; c) prostate cancer of Gleason Grade 6 or less with stable prostate-specific antigen levels; or d) cancer considered cured by surgical resection or unlikely to impact survival during the duration of the study

5.3 An indication for therapy initiation is required of all patients included on this trial. These listed below separately, for WM and MZL:

5.3.1 WM: Symptoms related to WM including: fever, night sweats, weight loss, fatigue; evidence of hyperviscosity; symptomatic lymphadenopathy or lymphadenopathy measuring 5 cm or larger; symptomatic hepatomegaly and/or splenomegaly; other symptomatic organ or tissue infiltration; peripheral neuropathy due to Waldenström's macroglobulinemia; or laboratory indications including symptomatic cryoglobulinemia, cold agglutinin anemia, immune hemolytic anemia or thrombocytopenia, nephropathy related to Waldenström's, amyloidosis related to Waldenström's, hemoglobin less than or equal to 10g/dL, platelet count less than or equal to 100,000/uL

5.3.2 MZL: Symptoms related to splenomegaly or lymphadenopathy; evidence of rapid disease progression; high tumor bulk (presence of 3 lymph node groups measuring 3 cm or more, or one node or conglomerate measuring 7 cm or more), cytopenias due to bone marrow infiltration or hypersplenism (hemoglobin less than or equal to 10 g/dL, platelet count less than or equal to 100,000/uL);

autoimmune hemolytic anemia or thrombocytopenia. Advanced stage disease, disease-related effusions, end organ compromise (iron deficiency anemia, organ infiltration), are also permissible criteria for initiation of therapy on this study.

6.0 REGISTRATION

Subjects will be registered by institutional research staff prior to the start of protocol therapy. A complete, signed study consent and HIPAA consent are required for registration.

7.0 TREATMENT PLAN

7.1 Each cycle of CFZ therapy is given every 28 days. Up to 6 cycles of CFZ therapy will be administered on protocol. Four weekly doses of weekly rituximab, then 3 additional doses of monthly rituximab, will be administered to select patients who do not respond to CFZ following the first 2 cycles. (Total 7 doses of rituximab).

We anticipate accrual of 24 patients over 18 - 24 months. Accrual will be limited to the first 9 patients initially then paused -- if needed-- to ensure the stopping rule (section 12.2 and 12.3) has not been reached before additional patients are accrued.

Plasmapheresis may be undertaken at any point in the study when clinically indicated. If protocol therapy is discontinued for disease progression requiring other treatment, patients may go on to receive other therapy at the discretion of their physician, but will be removed from this study.

7.1.1 Dose and Administration

Subjects with a BSA greater than 2.2 m² should receive a dose based upon a BSA of 2.2 m².

Carfilzomib will be administered 20 mg/m² over 30 minutes on Cycle 1 Day 1. If tolerated, the dose will be increased to 56 mg/m² on D8 and D15 of cycle 1. Escalation to 70 mg/m² starting with cycle 2 and beyond is allowed for all patients who have met criteria for ongoing therapy without delay due to toxicity, or need for dose modification as described in section 8.0. Cycles are repeated every 28 days. Do not administer as an IV bolus.

A maximum of 6 total cycles may be given.

7.1.1.1. If 20 mg/m² is not tolerated, it may be repeated with additional supportive care at clinical discretion for up to 4 weekly doses (C1 D1, C1 D8, C1 D15, and C2 D1) while reconsidering dose escalation. CFZ must then be escalated to 56 mg/m² for at least 2 doses, prior to increasing to 70 mg/m² as tolerated.

| Carfilzomib Therapy: Day 1, 8, and 15 of 28-day cycles | |
|---|--|
| Carfilzomib | Cycle 1-6 (actual dates may vary +/- 3 days) |
| Carfilzomib 20 mg/m ² over 30 minutes *with dexamethasone pre-medication | Cycle 1 Day 1 |
| Carfilzomib 56 mg/m ² over 30 minutes *with dexamethasone pre-medication for cycle 1 | cycle 1 Day 8 and 15 |
| Carfilzomib 70 mg/m ² over 30 minutes | All future days starting with Cycle 2 Day 1. |

Dose modification in response to toxicity is described under section 8.0 below.

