7.1.2 Required Premedication and Post-medication for Cycle 1, All Doses

For cycle 1: dexamethasone 8 mg orally or IV will be administered. Pre-medicate 30 minutes to 4 hours prior to all doses in cycle 1, and as needed with future cycles to reduce the incidence and severity of infusion reaction.

In addition, for cycle 1, 250 ml hydration using normal saline will be given pre-dose on day 1, 8, and 15 unless contraindicated due to clinician judgment. This hydration is optional for future cycles.

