8.2.8 Safety Considerations

Based upon the experience in the Phase 1 and 2 clinical studies with CFZ, the following observations are noted:

- A "first dose effect" has been seen, which is notable for fever, chills, rigors, and/or dyspnea occurring during the evening following the first day of infusion and an increase in creatinine, which may be the clinical sequelae of rapid tumor lysis and/or cytokine release.
- Should a "first dose" effect occur at any point during Cycle 1 or 2, treatment with high dose glucocorticoids (e.g. methylprednisolone 50–100 mg) is recommended. In addition, intravenous fluids, vasopressors, oxygen, bronchodilators, and acetaminophen should be available for immediate use and instituted, as medically indicated.
- Dexamethasone 8 mg PO/IV will be administered prior to all CFZ doses during the 1st cycle.
- If treatment-related fever, rigors, chills, and/or dyspnea are observed post any dose of CFZ after dexamethasone has been discontinued, dexamethasone should be re-started and administered prior to subsequent doses.
- CrCl changes are mostly transient, reversible, and non-cumulative. All subjects should be well hydrated. Clinically significant electrolyte abnormalities should be corrected prior to dosing with CFZ. Renal function must be monitored closely during treatment with CFZ. Serum chemistry values, including creatinine, must be obtained and reviewed prior to each dose of CFZ during Cycles 1 and 2. Carfilzomib must be held for subjects with a CrCl < 15 mL/min at any time during study participation.
- Subjects with active or suspected infection of any kind that required systemic treatment should not be dosed with CFZ until the infection has resolved and if being treated with anti-infective, the course of antibiotics has been completed.
- Carfilzomib treatment can cause nausea, vomiting, diarrhea, or constipation sometimes requiring the use of anti-emetics or anti-diarrheals. Fluid and electrolyte replacement should be administered to prevent dehydration.

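### Required dexamethasone and saline are tied to cycle 1, so a patient held at 20 mg/m² for three doses meets the first 56 mg/m² dose in cycle 2, where neither is required

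*Combined protocol and SAP*

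**What the plan says.** Carfilzomib is given on days 1, 8 and 15 of 28-day cycles. On the standard schedule (section 7.1.1) the dose is 20 mg/m² at C1D1, 56 mg/m² at C1D8 and C1D15, and 70 mg/m² from C2D1.

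Section 7.1.1.1 covers patients who do not tolerate 20 mg/m². That dose may be repeated, with extra supportive care as the clinician sees fit, "for up to 4 weekly doses (C1 D1, C1 D8, C1 D15, and C2 D1) while reconsidering dose escalation". The dose must then go to 56 mg/m² for at least two doses before any rise to 70 mg/m².

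The cover rules are tied to the cycle:

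- Dexamethasone 8 mg, section 7.1.2: "Pre-medicate 30 minutes to 4 hours prior to all doses in cycle 1, and as needed with future cycles".
- Dexamethasone, the 56 mg/m² row of the 7.1.1 table: "with dexamethasone pre-medication for cycle 1".
- Dexamethasone, section 8.2.8: "Dexamethasone 8 mg PO/IV will be administered prior to all CFZ doses during the 1st cycle".
- Saline, section 7.1.2: 250 mL before each cycle 1 dose unless the clinician judges it contraindicated. After that, "This hydration is optional for future cycles".

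Section 8.2.8 also has a restart rule. If treatment-related fever, rigors, chills or dyspnea is seen "post any dose of CFZ after dexamethasone has been discontinued, dexamethasone should be re-started and administered prior to subsequent doses".

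**The concern.** Section 7.1.1.1 names C2D1 as a possible 20 mg/m² day, so it foresees the step to 56 mg/m² falling in cycle 2. The premedication rule was not carried forward with it. A patient who tolerated the first dose takes the step with required dexamethasone and saline. A patient who needed three doses at 20 mg/m² takes the same step with neither required.

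What is at stake is patient safety at one dose step. Appendix 20.1 describes a first-dose effect at 27 mg/m², a level that the step from 20 to 56 mg/m² crosses, and credits hydration and low-dose dexamethasone with nearly abolishing it in later studies. Section 8.2.8 does not confine the problem to cycle 1: should a first dose "effect occur at any point during Cycle 1 or 2, treatment with high dose glucocorticoids" is recommended. That is treatment after the event, not prevention.

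**Working it through.** The plan gives no figure to reproduce. The check traces the dosing calendar against the cover rules, assuming that no dose is missed or held.

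**Inputs.** Dose slots in order: C1D1, C1D8, C1D15, C2D1, C2D8, C2D15 (section 7.1.1). One to four doses at 20 mg/m², then at least two at 56 mg/m² (7.1.1.1). Required cover per cycle 1 dose: 8 mg dexamethasone and 250 mL saline (7.1.2). Required cover per later dose: none.

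**Formulae.** Let k be the number of 20 mg/m² doses. The first two 56 mg/m² doses occupy slots k+1 and k+2. Cycle 1 holds slots 1 to 3, so the number of these doses inside cycle 1 is n = max(0, min(2, 3 − k)). Required cover over them is 8n mg and 250n mL.

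| k | First two 56 mg/m² doses | n | Required dexamethasone | Required saline |
|---|---|---|---|---|
| 1 (standard) | C1D8, C1D15 | 2 | 16 mg | 500 mL |
| 2 | C1D15, C2D1 | 1 | 8 mg | 250 mL |
| 3 | C2D1, C2D8 | 0 | 0 mg | 0 mL |
| 4 | C2D8, C2D15 | 0 | 0 mg | 0 mL |

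The step is 56/20 = 2.8-fold in every row. With k = 2 the first 56 mg/m² dose still has required cover; only the second does not.

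**Does the restart rule close the gap?** It needs a listed reaction to a dose given after dexamethasone was stopped. With k = 3 all earlier doses were in cycle 1 and premedicated, so the rule cannot be triggered before C2D1. With k = 4 it can restore dexamethasone at C2D8, but only if a reaction follows a C2D1 dose given without it. It does not restore saline on either path.

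**Do other provisions close it?** Section 8.2.8 states: "Serum chemistry values, including creatinine, must be obtained and reviewed prior to each dose of CFZ during Cycles 1 and 2". That is monitoring. Its advice that subjects be well hydrated gives no volume, route or timing. Section 9.1 permits corticosteroid premedication in later cycles where clinically indicated, and permission is not a requirement. The extra supportive care in 7.1.1.1 attaches to the repeated 20 mg/m² doses, not to the escalation.

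**The case against.** The strongest reply is that discretion is adequate here. These patients have already been singled out for extra supportive care. The as-needed clause exists to reduce infusion reactions, and a patient who reacted at 20 mg/m² is its plainest case. Nothing obliges anyone to stop dexamethasone after cycle 1. This stands as a reason to expect few uncovered steps. It does not explain why the same step is covered by requirement on the standard schedule and left to judgment here.

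Second, poor tolerance of 20 mg/m² is not defined as an infusion reaction. It could be hypertension or a cardiac symptom, and section 2.1 raises routine IV fluids as a possible contributor to cardiac toxicity. This stands, and it means that any requirement needs a clinician exception for dexamethasone as well as saline.

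Third, the standard step from 56 to 70 mg/m² at C2D1 also has no required cover, so a cycle-based rule is at least consistent. But that step is 70/56 = 1.25-fold and follows two covered doses at 56 mg/m².

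Fourth, a patient given four doses at 20 mg/m² might already meet removal criterion 7.3.2. This stands, so the C2D8 case is conditional. The C2D1 case does not depend on it.

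A reader might also infer that an uncovered C2D1 dose could lead to removal under 7.3.2, because after three 20 mg/m² doses it is the only dose above that level among the first four. The text does not support this. The criterion presupposes that supportive care has been taken as far as it can go, and a patient given neither measure, without a contraindication, would hardly qualify.

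**Conclusion.** The gap is real but narrow: requirement against discretion at one dose step. It certainly arises after three 20 mg/m² doses (first 56 mg/m² dose at C2D1), and after four (C2D8) only if the patient stays on treatment under 7.3.2. Required cover over the first two 56 mg/m² doses is then 0 mg and 0 mL, against 16 mg and 500 mL on the standard schedule. The number of patients affected is not given and is probably a small part of the 24 planned.

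Three wider readings should be resisted:

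- Not every patient who fails to tolerate 20 mg/m² loses cover; those given two such doses keep it for the first step.
- The documents do not show harm from a later uncovered step. The appendix data come from twice-weekly dosing and concern the first infusion, whereas these patients have already had three premedicated doses.
- There is no effect on the Simon design, and no established effect on removals under 7.3.2.

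This is a cheap improvement, not a flaw that threatens the trial. The conclusion rests on doses being given on schedule and on 7.1.2 being applied as written.

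**What to change.** In section 7.1.2, the 56 mg/m² row of the 7.1.1 table and the dexamethasone line of 8.2.8, state: dexamethasone 8 mg and 250 mL normal saline, each unless contraindicated by clinician judgment, are given before all cycle 1 doses and before the first two 56 mg/m² doses, in whatever cycle they fall.

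The extra required cover is 8 × (2 − n) mg and 250 × (2 − n) mL. Cycle 1 already requires 3 × 8 = 24 mg and 3 × 250 = 750 mL, which gives these new totals:

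| 20 mg/m² doses | Extra dexamethasone (new total) | Extra saline (new total) |
|---|---|---|
| 1 | 0 (24 mg) | 0 (750 mL) |
| 2 | 8 mg (32 mg) | 250 mL (1000 mL) |
| 3 | 16 mg (40 mg) | 500 mL (1250 mL) |
| 4 | 16 mg (40 mg) | 500 mL (1250 mL) |

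Standard-schedule patients receive nothing extra. Affected patients receive a little more steroid before the post-cycle-2 response assessment of single-agent carfilzomib, and a fluid load that the contraindication clause limits. The wording also gives cycle 1 dexamethasone a clinician exception that it does not have now. If the sponsor wants that requirement unchanged, the dexamethasone exception can be confined to the cycle 2 doses.

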7.1.2 Required Premedication and Post-medication for Cycle 1, All Doses

For cycle 1: dexamethasone 8 mg orally or IV will be administered. Pre-medicate 30 minutes to 4 hours prior to all doses in cycle 1, and as needed with future cycles to reduce the incidence and severity of infusion reaction.

In addition, for cycle 1, 250 ml hydration using normal saline will be given pre-dose on day 1, 8, and 15 unless contraindicated due to clinician judgment. This hydration is optional for future cycles.

7.1.3 Supportive Care

Consider antiviral prophylaxis for patients who have a history of herpes zoster infection, using Acyclovir 800 mg PO daily. Additional prophylaxis or monitoring for infections may be used for subjects deemed at high risk of bacterial, viral, or fungal infections.

Premedication for rituximab will be administered according to standard, institutional guidelines.

7.1.4 Blood pressure monitoring at least twice per week during cycle 1 will be conducted for patients with pre-existing systolic hypertension on medical therapy, or any who develop grade 3 hypertension or require the addition of antihypertensive therapy during cycle 1.

7.2 Administration of Rituximab to CFZ Non-responders

Subjects who fail to achieve at least a 25% M-protein reduction based on SPEP m-protein quantification for WM, or partial response for MZL based on imaging, following 2 cycles of CFZ therapy will receive rituximab concurrent with CFZ.

7.2.1 Note: the bone marrow aspirate / biopsy after cycle 2 is exploratory and not to be used for response assessment or determination regarding rituximab.

7.2.2 IV Rituximab, pre-medications, and hypersensitivity management will be administered according to standard institutional or pharmacy guidelines.

| RITUXIMAB weekly x 4 doses (cycle 3) then monthly (cycles 4-6) | | | | |
|---|---|------|------|------|
| Treatment | Cycle 3-6 for patients not responding to CFZ (actual dates may vary +/- 3 days; cycle timing refers to CFZ) | | | |
| | C3 D1,8,15,22 | C4D1 | C5D1 | C6D1 |
| Rituximab 375 mg/m ² | X, X, X, X | X | X | X |

7.2.3 Following rituximab administration for WM, weekly laboratory evaluation of IgM levels (to evaluate for Ig M flare for clinical and study data purposes) is required. (See section 10, study calendar). As clinically indicated, viscosity measurement and other evaluation or management of hyper-viscosity syndrome, including plasmapheresis, should be undertaken. Weekly evaluation will continue until no longer clinically indicated.

7.3 Criteria for removal from protocol treatment: (Note: Subjects discontinued from CFZ will not receive rituximab on study.)

7.3.1 Symptomatic progression of disease after completion of at least 4 total cycles of CFZ therapy (with or without rituximab). IgM flare following rituximab (even if requiring plasmapheresis), or biochemical progression alone do not require removal from protocol treatment.

- 7.3.2 Inability to tolerate more than 20 mg/m² of CFZ during the first 4 doses of therapy, despite maximal supportive care.
- 7.3.3 Development of excess hematologic toxicity not responding to supportive care or persisting despite dose reductions—as outlined in Section 8.0
- 7.3.4 Development of any other unacceptable toxicities unless prophylactic measures can be taken for subsequent cycles.
- 7.3.5 Missed doses will not be replaced during a cycle. If a subject misses more than 2 doses of any cycle for reasons other than toxicity, the subject will be discontinued.
- 7.3.6 Delay of a treatment cycle for more than 4 weeks due to adverse events
- 7.3.7 Completion of protocol treatment (maximum of 6 cycles, or 18 doses of CFZ).
- 7.3.8 The patient may withdraw from the treatment at any time for any reason.
- 7.3.9 Subjects may be removed from treatment in the event of study termination for any reason, as described under section 18.0.

7.4 Early Termination for Futility

As in section 12.2, the study will be stopped if two or fewer of the first 9 patients respond after cycle two. Previously enrolled subjects will continue on study as per the treatment plan (Section 7).

8.0 REQUIREMENTS TO BEGIN A NEW CYCLE AND DOSE ADJUSTMENT GUIDELINES

Parameters for retreatment and treatment modifications are as follows. Patients may be reduced to dose level -1 or 2, without impact on future enrolled patients (who will initiate the Starting Dose.)

Dose levels are as follows:

- Starting Dose: CFZ 20 mg m² (C1D1) then 56 mg/m² (cycle 1 day 8 and 15), then 70 mg/m² (all future weekly doses)
- Dose level -1: CFZ 56 mg/m²
- Dose level -2: CFZ 27 mg/m²

8.1 Requirements to Begin a New Cycle

Subsequent cycles of CFZ therapy will not begin until the ANC is $\geq 500/\mu\text{L}$ and the platelet count is $\geq 50,000/\mu\text{L}$ unless related to disease infiltration. For patients with cytopenias related to marrow infiltration, return to the subject's baseline ANC and platelet count is adequate to resume a subsequent cycle.

Treatments will also be delayed for reasons described in Section 8.2, or for clinically significant Grade 2 or 3 adverse events and unrelated Grade 4 adverse events at the discretion of the treating physician, or Principal Investigator.

Therapy may be delayed a maximum of 4 weeks until these values are achieved for Day 1 of each cycle. Hematopoietic growth factors and blood product support are allowed. There are no study parameters required for initiation of rituximab. Rituximab and CFZ should be started simultaneously during Cycle 3 for subjects who qualify (section 7.2), and are deemed fit for rituximab therapy by the investigator.

Subjects who undergo dose reduction to dose level -2 may not undergo further dose changes.

8.2 Specific management of toxicities are as follows:

8.2.1 Neutropenia

- For the first instance of ANC $\leq 1000/\mu\text{L}$ with complications, or ANC $\leq 500/\mu\text{L}$ unless related to disease infiltration, GCSF support will be initiated.
- For the second such instance despite GCSF support, CFZ will be reduced to dose level -1.

- For the third instance or failure to achieve ANC 500/uL in 4 weeks, despite GCSF support, the subject will be reduced to dose level -2. If severe neutropenia persists, patients will be removed from study.
- For subjects with disease infiltration, GCSF support may be used at the discretion of the investigator. For ANC \leq 500/uL without complications and attributable to disease infiltration, return to a subject's baseline is required and adequate, to start a new cycle.

8.2.2 Thrombocytopenia

- For the first instance of platelets \leq 25,000/uL, or at the discretion of the investigator for patients deemed at risk of bleeding complications, CFZ will be reduced to dose level -1.
- For the second instance of platelets \leq 25,000/uL or failure to achieve platelet count of 25,000/uL or greater after 4 weeks, CFZ will be reduced to dose level -2. If further decreases are required, the patient will be removed from study therapy.

8.2.3 Anemia

There is no pre-specified dose reduction requirement for anemia, but growth factors or transfusion (where appropriate) may be used and CFZ may be dose reduced as clinically indicated.

8.2.4 Dose Reductions for Non-Hematologic Toxicities

- Study drug should be held for \geq Grade 3 events until resolved to \leq Grade 1 or return to baseline, unless otherwise noted in the table below.
- All cases of grade 3 or greater systolic HTN (SBP >160) will require action per protocol including holding study drug and management /dosing only once BP is controlled.
- After resolution of the event to \leq Grade 1 or return to baseline, if the adverse event was not treatment-related, subsequent treatment with CFZ may resume at full dose. If the event was treatment-related, subsequent treatment with CFZ will resume at dose level -1. If toxicity continues or recurs, a 2nd CFZ dose reduction to dose level -2 may be permitted the discretion of the investigator. No more than two dose reductions will be permitted in an individual subject on study. If toxicity continues or recurs after two dose reductions, the subject should be removed from study.
- Dose adjustment guidelines for non-hematologic toxicities are summarized in the following table:

| Symptom | Recommended Action Carfilzomib |
|---|--|
| Allergic reaction/hypersensitivity Grade 2 – 3 | Hold until \leq Grade 1, reinstitute at full dose. |
| Grade 4 | Discontinue |
| Grade 3 or higher systolic HTN | Hold until grade 2 or less, initiate medical management if clinically indicated, dose only when resolves or improves to Grade 2 or less. |
| Tumor lysis syndrome (\geq 3 of following: \geq 50% increase in creatinine, uric acid, or phosphate; \geq 30% increase in potassium; \geq 20% decrease in calcium; or \geq 2-fold increase in LDH | Hold CFZ until all abnormalities in serum chemistries have resolved. Reinstigate at full doses. |

| | |
|---|--|
| Infection Grade 3 or 4 | Hold CFZ until systemic treatment for infection complete. If no neutropenia, restart at full dose. If neutropenic, follow neutropenic instructions. |
| Herpes zoster or simplex of any grade | Hold CFZ until lesions are dry. Re institute at full dose |
| Gr 2 treatment emergent neuropathy with pain | Continue to dose. If neuropathy persists for more than two weeks hold CFZ until resolved to \leq Gr 2 without pain. Then restart at 1 dose decrement |
| Grade 3 neuropathy | Withhold CFZ until resolved or returned to baseline. Subsequent treatment with carfilzomib should resume at a lower dose level. |
| Grade 4 neuropathy | Discontinue |
| Renal Dysfunction CrCl \leq 15 mL/min | Hold until CrCl $>$ 30 mL/minute; restart at 1 dose decrement |
| Congestive heart failure | Any subject with symptoms of congestive heart failure, whether or not drug related, must have the dose held until resolution or return to baseline, after which treatment may continue at a reduced dose, or the subject may be withdrawn from the study. If this results in a delay of treatment for more than 4 weeks, the subject will be withdrawn from the study. |
| Other non-hematologic toxicity assessed as CFZ-related \geq Grade 3 | Hold dose until toxicity resolves to \leq Grade 1 or baseline. Restart at 1 dose decrement. |

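### For toxicities before 70 mg/m² is reached, the dose-modification passages conflict: level -1 equals the cycle 1 day 8/15 dose, and text and table can point to different doses

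*Combined protocol and SAP*

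**What the plan says.** **Planned doses.** Section 7.1.1 states "Carfilzomib will be administered 20 mg/m² over 30 minutes on Cycle 1 Day 1" and then, provided that dose is tolerated, "the dose will be increased to 56 mg/m² on D8 and D15 of cycle 1". From cycle 2 the dose may rise to 70 mg/m² for patients with no toxicity delay and no need for a dose modification.

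**Dose levels.** Section 8.0 has "Dose level -1: CFZ 56 mg/m²" as the first step below the starting dose and "Dose level -2: CFZ 27 mg/m²" as the one after it. The starting dose itself is defined as a sequence and not as a single figure: "Starting Dose: CFZ 20 mg m² (C1D1) then 56 mg/m² (cycle 1 day 8 and 15), then 70 mg/m² (all future weekly doses".

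**Text of section 8.2.4.** Once a non-hematologic event has resolved: "If the event was treatment-related, subsequent treatment with CFZ will resume at dose level -1". The sentence makes no distinction by cycle or by the dose at which the event occurred. The section then calls level -2 the second reduction, caps reductions at two per patient, and directs removal if toxicity persists after both.

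**Table of section 8.2.4.** Grade 3 neuropathy calls for resumption at a lower level. Painful grade 2 neuropathy that persists, severe renal dysfunction, and other related events of grade 3 or above call for one decrement. For the last of these the wording is "Hold dose until toxicity resolves to \leq Grade 1 or baseline. Restart at 1 dose decrement". The size of a decrement is not defined.

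**Hematologic toxicity.** Sections 8.2.1 (second instance of neutropenia) and 8.2.2 (first instance of thrombocytopenia) also describe a move to level -1 as a reduction.

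**Day 1 intolerance.** Section 7.1.1.1 says of the 20 mg/m² dose that "it may be repeated with additional supportive care at clinical discretion for up to 4 weekly doses", followed by a required rise to 56 mg/m².

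**Discretion.** Section 8.2.7 permits modifications other than those written.

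**The concern.** The dose levels work as a descending ladder only for a patient already at 70 mg/m². In cycle 1 no patient has reached that dose. For an event at 56 mg/m², the step that the protocol names as a reduction leaves the dose where it was. For an event at 20 mg/m², neither level -1 nor level -2 lies below the dose just given.

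Three things are at stake:

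- **Safety.** A default meant to lower exposure after a related toxicity may not do so, and two investigators could read section 8.2.4 and give the same patient different doses.
- **Retention on treatment.** A step with no change in dose may use up one of the two permitted reductions and bring removal closer.
- **Consistency.** Cycle 1 toxicity is a realistic case. Section 8.2.8 describes a first-dose effect. Appendix 20.1 reports one possibly related grade 3 renal failure on day 2 of cycle 1 among eight patients at 20 mg/m², although on a twice-weekly schedule.

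**Working it through.** The protocol gives no figure of its own to reproduce here. The check compares each fixed level with the dose in force when the event occurs.

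**Inputs** (sections 7.1.1 and 8.0): 20 mg/m² on cycle 1 day 1; 56 mg/m² on cycle 1 days 8 and 15; 70 mg/m² afterwards; level -1 = 56 mg/m²; level -2 = 27 mg/m².

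**Formula:** change = (level / dose at onset) - 1.

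| Dose at onset | Level -1 (56 mg/m²) | Level -2 (27 mg/m²) |
|---|---|---|
| 70 (cycle 2 onward) | 56/70 - 1 = -20% | 27/70 - 1 = -61.4% |
| 56 (cycle 1 days 8, 15) | 56/56 - 1 = 0% | 27/56 - 1 = -51.8% |
| 20 (cycle 1 day 1) | 56/20 - 1 = +180% | 27/20 - 1 = +35% |

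**Step 1: events on day 8 or 15.** The text of section 8.2.4 gives 56 mg/m², which is no change. Because the next step is named the second reduction, this one counts as the first. The path is 56 to 56 to 27, so only one of the two counted steps lowers the dose. From 70 the path is 70 to 56 to 27, and both do.

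**Step 2: text against table.** Suppose a patient has a related grade 3 event after day 8 that falls in the table's row for other toxicities. Under the text, the dose on resumption is level -1, 56 mg/m². Under the table it is one decrement. Read as a move to level -1, that is again 56 mg/m². Read as one step down from the current dose, it is 27 mg/m². The two readings differ by 56/27 = 2.07, about twofold. The grade 3 neuropathy row asks for a lower level; level -1 is lower by label, but in mg/m² it equals the dose at onset.

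**Step 3: events on day 1.** Three passages apply to the same patient:

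- Section 7.1.1 makes the rise to 56 mg/m² conditional on tolerance.
- Section 7.1.1.1 allows 20 mg/m² to be repeated, at clinical discretion.
- Section 8.2.4 says, without condition, that treatment resumes at level -1, which is 56 mg/m².

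The first two can hold the dose at 20 mg/m²; the third, taken literally, does not. No passage sets an order of precedence.

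**Step 4: hematologic events.** Sections 8.2.1 and 8.2.2 use the same level, so a move to level -1 from 56 mg/m² is again a 0% change described as a reduction.

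**The case against.** The best defense is that section 8.0 defines the starting dose as the whole 20/56/70 sequence. Level -1 is then a step down from the planned regimen: a patient placed on it stays at 56 mg/m² while others go to 70. That reading is coherent for a day 8 or 15 event under the text of section 8.2.4, and against the planned 70 mg/m² it is a 20% lowering. It does not settle the matter. Section 7.1.1 already withholds the rise to 70 mg/m² from such patients, so the step adds little. It also leaves the decrement undefined, and it cannot explain a day 1 event.

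A reader might infer that the protocol orders a 2.8-fold increase (56/20) after a day 1 toxicity. The documents do not support that. It follows only if the general sentence in section 8.2.4 overrides the tolerance condition in section 7.1.1 and the specific provision in section 7.1.1.1. Section 7.3.2 also provides for removal of patients who cannot tolerate more than 20 mg/m² over the first four doses. What stands is a conflict without a stated precedence.

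A reader might also extend the point to every related event of grade 3 or above. That is too wide. The rows for hypersensitivity, systolic hypertension, tumor lysis, infection, herpes infection and grade 4 neuropathy carry their own actions, and section 8.2.8 has separate management for first-dose effects.

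Finally, the table's actions are labeled as recommended, and section 8.2.7 allows departures. The rule is therefore a default and not a mandate. Permission to depart does not make the default consistent.

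**Conclusion.** The concern holds as an unreconciled conflict limited to toxicities that occur before 70 mg/m² is reached. After a day 8 or 15 event, the text of section 8.2.4 gives a 0% change and counts it as the first of two reductions. The text and table can lead to 56 or 27 mg/m² for the same patient. For a day 1 event, sections 7.1.1, 7.1.1.1 and 8.2.4 disagree and none is said to govern. From 70 mg/m² onward, level -1 is a true 20% reduction.

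This rests on reading level -1 as the fixed 56 mg/m² of section 8.0 and on taking the table rows with their own action as governing their events. All 24 planned patients are due to receive cycle 1, but that counts exposure and not patients affected; the documents give no rate of qualifying cycle 1 events in this trial.

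It might be tempting to add that the tolerability objective becomes uninterpretable. Section 1.2.1 asks only for safety and tolerability, and section 12 defines no count of dose reductions, so the documents do not support that. The point is worth correcting because it concerns a safety instruction and the correction is cheap.

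**What to change.** Reconcile sections 7.1.1, 7.1.1.1, 8.0, 8.2.1, 8.2.2 and 8.2.4 (text and table) for events before 70 mg/m² is reached. In doing so:

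- define what one decrement means, and make the text and table of section 8.2.4 agree;
- state which section governs toxicities in cycle 1, including after the day 1 dose;
- state whether resuming at an unchanged dose uses one of the two permitted reductions.

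The choice of dose and of rule is for the sponsor's clinicians; none is proposed here. The cost is a wording amendment, with no effect on sample size, the response decision rule or study procedures.
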